## 7.5 Study Documentation and Record Keeping

## 7.5.1 Retention of Documents

The sponsor and the participating site investigators should maintain appropriate records as described in the protocol. At the site level, this will include the study protocol and any amendments, ethics correspondence and approval, patient log with a duly filled in checklist, a copy of the patient enrolment form and patient or surrogate consent forms (see section 5.3) They will also maintain their part of the trial database. At the sponsor/central level, this will include the study protocol and any amendments, ethics approval documents from sites, trial database along with the last page of the signed consent forms, copies of any communication with Health Canada and site initiation and training logs including logs of all educational efforts described in section 7.4. Any or all of these files may be stored electronically. The sponsor (and any participating site investigators) must keep these documents on file for 25 years after completion or discontinuation of the study or as deemed by data sources such as CIHI After that period of time the documents may be destroyed, subject to local regulations.

## 7.5.2 Source Documents

Any participating site investigators shall supply the sponsor on request with any required data from the study documentation or clinic records. In case of special problems and/or governmental

queries or requests for audit inspections, it is also necessary to have access to the complete study records, provided that patient confidentiality is protected.

## 7.5.3 Inspections

The sponsor understands that documents for this trial should be made available to appropriately qualified personnel or to health authority inspectors after appropriate notification.

## 7.6 Data Safety Monitoring Committee

The independent Data Safety and Monitoring Committee (DSMC) will be constituted in consultation with the steering committee and include clinicians, a nurse representative, a statistician and a patient representative. The DSMC will meet by teleconference to review safety data after each cohort of approximately 500 participants is enrolled. To prevent bias at the trial and investigator level, all interim results on safety will only be available to the DSMC. Stopping rules based on safety alone will be specified in the DSMC charter. Mechanisms to ensure this will be detailed in the DSMC Charter. The Data Safety and Monitoring Committee will be constituted based on the DAMOCLES charter format. The DSMC will meet by teleconference to review safety data after each 1/3rd cohort of subjects are enrolled.

# 7.7 End of trial

End of trial is defined as when data on the last patient recruited into the trial is completed. The trial will end when the trial steering committee agrees that one or more of the following situations applies:

- 1. The planned sample size has been achieved
- 2. The DSMC advises discontinuation because of safety concerns
- 3. New information makes it inappropriate to continue to randomise patients to one or other arm of the trial
- 4. Recruitment is so poor that completion of the trial is considered difficult

## 7.8 Ancillary Studies, Co-Enrollment and Publication Policy

The trial steering committee will constitute a publication committee that will include site principal investigators and the lead statistician. Policies will be detailed in a Publication Policy Charter. Ancillary studies will also be vetted by the trial steering committee and a decision made on merits of the proposed study.

Patients enrolled in the AcT RRCT are eligible to be enrolled into the EASI-TOC RCT. This study targets a subgroup of patients with ischemic stroke who have what are called tandem occlusions. EASI-TOC aims to determine whether, in addition to thrombectomy to recanalize intracranial occlusion (standard of care); patients with a tandem occlusion should also be acutely treated with a stent to revascularize their cervical internal carotid artery during the thrombectomy procedure. Inclusion in the AcT and EASI-TOC trials do not subject patients to increased risk. No multiplicative biological interaction between the interventions studied in both studies is expected. Patients are randomized just before or at the start of the thrombectomy procedure, once the carotid lesion is

confirmed by angiography. The allocation is 1:1 (stent versus no stent). Both approaches lesion is confirmed by angiography. The allocation is 1:1 (stent versus no stent). Both approaches used in EASI-TOC are considered standard care and used in daily clinical practice. Neither approach is therefore experimental. The pragmatic design of the two studies prevents patients from being subjected to additional study specific investigations, procedures or clinical follow-up beyond usual care.

It is estimated that < 5% of patients eligible for enrolment into the AcT RRCT will also be candidates for EASI-TOC (approximately 60-80 patients out of a planned 1600 patients to be included in AcT). Approximately 1/3rd of subjects eligible for AcT will likely undergo endovascular thrombectomy i.e. 533 subjects.

Statistical simulations with different possible interaction scenarios suggest limited effect on outcomes within both studies. Outcome ascertainment in EASI-TOC does not influence or affect outcome ascertainment in AcT. There are precedents in medicine for including patients in more than one randomized trial, especially in the fields of oncology and critical care and more recently with COVID-19.

On request, the trial steering committee will follow the same processes above to determine if coenrolment will be allowed for other trials. The process will involve consultation with statiscians, ethics boards, patient focus groups and with Health Canada.

## 7.9 Data sharing plan

The Trial Steering Committee will follow the CIHR guidelines on public access to trial results. Upon completion of trial, a public use database will be prepared by stripping any and all personal identifiers. The data files will be distributed along with the data dictionary and a brief instruction ("Readme") file. These data files will be made available to the public only after all major manuscripts (including secondary analysis papers) of the trial are accepted for publication.

## APPENDIX

Table 1: List of Adverse Events. (Stroke. 2014; 45: 2677-2682)

Adverse Event (AE)	Incidence	Serious Adverse Event	Incidence
	(AEs/	(SAE)	(AEs/

		QUICR & OPTIMIST	
	1,000		1,000
	patients)		patients)
Pyrexia	160.69	Stroke in Evolution	11.2
Headache	137.32	Pneumonia	16.8
Urinary Tract Infection	87.45	Ischemic Cerebral Infarction	21.7
Anxiety	90.04	Brain Edema	26.0
Constipation	88.48	Cardiac Failure	29.4
Hypertension	75.67	Myocardial Infarction	32.3
Pneumonia	65.63	Cerebral Hemorrhage	34.8
Nausea	68.92	Aspiration Pneumonia	37.3
Vomiting	67.88	Respiratory Failure	39.5
Stroke in Evolution	60.95	Hemorrhagic Transformation	41.7
Hypokalemia	57.32	Pulmonary Embolism	43.7
Atrial Fibrillation	52.81	Atrial Fibrillation	45.5
Depression	44.16	Urinary Tract Infection	47.2
Somnolence	32.38	Pulmonary Edema	48.7
Insomnia	39.31	Cerebrovascular Disorder	50.2
Cardiac Failure	33.94	Cardiac Arrest	51.7
Hypotension	36.36	Carotid Artery Disease	53.1
Hematuria	35.15	Sepsis	54.3
Brain Edema	30.13	Angina Pectoris	55.5
Pain	25.97	Hypotension	56.6
Hemorrhagic	28.92	Coma	57.7
Transformation			
Edema Peripheral	25.80	Pyrexia	58.8
Bradycardia	30.48	Renal Failure	59.8
Ecchymosis	25.97	Headache	60.7
Diarrhea	29.61	ICP increased	61.6
Ischemic Cerebral	28.57	Respiratory Tract Infection	62.5
Infarction		1 5	
Cerebral Hemorrhage	24.59	Bradycardia	63.3
Angina Pectoris	26.32	Transient Ischemic Attack	64.1
Aspiration Pneumonia	24.76	Gastrointestinal Hemorrhage	64.9
Cough	23.72	Hypertension	65.6
Dyspnea	24.94	Hemorrhagic Cerebral	66.3
5 1		Infarction	
Hyperglycemia	24.76	Somnolence	67.1
Tachycardia	24.24	Cerebral Incarceration	67.6
Musculoskeletal Pain	23.72	Deep Vein Thrombosis	68.2
Back Pain	24.07	Syncope	68.8
Confusional State	20.61	Depression	69.3
Respiratory Tract Infection	19.05	Hematuria	69.7
Rash	18.18	Vomiting	70.2
Purpura	11.77	Cerebrovascular Accident	70.6

		QUICR & OPTIM	AISE
Pulmonary Edema	17.66	Convulsion	71.0
Urinary Incontinence	13.16	COPD	71.4
Myocardial Infarction	16.80	Dyspnea	71.8
Respiratory Failure	15.24	Anemia	72.2
Anemia	14.72	Aspiration	72.5
Abdominal Tenderness	17.49	Bronchitis Acute	72.9
Rhonchi	12.64	Cardiopulmonary Failure	73.2
Lung Crepitation	12.47	Constipation	73.6
Extrasystoles	13.16	Epilepsy	73.9
Restlessness	16.10	Abdominal Tenderness	74.2
Bronchitis Acute	14.89	Dehydration	74.6
Pulmonary Congestion	11.77	Ileus	74.9
Urinary Retention	13.51	Septic Shock	75.2
Renal Failure	12.29	Colon Neoplasm	75.5
Conjunctivitis	11.43	Rectal Hemorrhage	75.8
Carotid Artery Disease	11.43	Tachycardia	76.1
Dizziness	12.81	Thrombosis	76.4
Phlebitis	12.47	Ventricular Tachycardia	76.7
Edema	11.77	Arrhythmia	76.9
Accident and/or Injury	7.45	Coronary Artery Disease	77.2
Hematoma	11.77	Multi-organ Failure	77.4
Erythema	12.47	Neurological Symptom	77.7
Sleep Disorder	10.91	Respiratory Arrest	77.9
Pulmonary Embolism	10.91	Shock	78.2
Ventricular Tachycardia	11.60	Urosepsis	78.5
Cerebrovascular Disorder	6.75	Cardiogenic Shock	78.7
Hypomagnesemia	11.26	Hip Fracture	78.9
Bronchospasm	9.52	Melena	79.1
Body Temperature	11.60	Nausea	79.4
Increased			
Dysphagia	8.48		
Convulsion	9.52		
Pain in Extremity	10.74		
Coma	7.62		
Sweating Increased	9.52		
Sepsis	8.83		
Breath Sounds Decreased	7.62		
Arthralgia	8.31		
Urine Output Decreased	9.35		
Leucocytosis	6.58		
Apnea	9.00		
Cardiac Arrest	8.31		
Syncope	9.18		
Hemorrhagic Cerebral	7.79		
			I

	1	QUICR & OPTIMISE	
Infarction			
Pleural Effusion	7.27		
Fatigue	9.00		
Neck Pain	8.66		
Rash Erythematous	5.71		
Hyponatremia	8.48		
Shoulder Pain	7.79		
Hypercholesterolemia	7.45		
Dehydration	6.93		
Procedural Complication	7.62		
Diabetes Mellitus	7.97		
Arrhythmia	6.93		
Edema Legs	6.23		
Fecal Incontinence	6.93		
Нурохіа	5.89		
Hiccups	6.41		
Neurological Symptom	6.23		
Lung Disorder	5.54		
Epistaxis	7.45		
Decubitus Ulcer	7.27		
Sick Sinus Syndrome	6.06		
Hyperlipidemia	6.06		
Gastrointestinal	6.23		
Hemorrhage			
Infusion Site Reaction	6.41		
Hypocalcemia	6.06		
Epigastric Pain	5.54		
Muscle Spasms	6.41		
Tachycardia	6.23		
Supraventricular			
Pruritus	5.89		
Deep Vein Thrombosis	5.54		
Candidiasis	4.68		
Atrial Flutter	5.54		
ICP Increased	6.06		
Transient Ischemic Attack	5.19		
Epilepsy	5.71		
Atelectasis	4.50		
Wheezing	5.89		
Melena	3.98		
Hyperthermia	4.85		
Hepatic Enzyme Increased	5.19		
Fall	5.71		
Protein C Increased	5.54		
		1	1

Injection Site Reaction	3.64	
ALT Increased	4.50	
Speech Disorder	3.29	
COPD	4.16	
Sensory Disturbance	4.16	
Hyperkalemia	4.85	
Bacterial Infection	3.46	
Oral Candidiasis	4.68	
Excoriation	4.33	

ICP indicates intracranial pressure; COPD: chronic obstructive pulmonary disease; ALT: alanine transaminase.

Underlined SAEs are events not found on the original adverse event list. ICP indicates intracranial pressure; COPD: chronic obstructive pulmonary disease.

**Table 2:** Summary Characteristics of the 4 phase II trials and the one phase III trial to date comparing intravenous tenecteplase to intravenous alteplase in patients with acute ischemic stroke

Version 2.0

44

	TNK-S2B	Australian TNK	ATTEST	Nor-Test	EXTEND-IA TNK
Countries	United States	Australia	Scotland	Norway	Australia and New Zealand
Number of sites	10	3	1	13	13
Patients, n	112	75	96	1100	202
TNK Dose(s)	0.1 mg/kg	0.1 mg/kg	0.25 mg/kg	0.4 mg/kg	0.25 mg/kg
	0.25 mg/kg	0.25 mg/kg			
	0.4 mg/kg				
Age, mean (SD)	69.1 (16.6)	70 (8.23)	71 (12.5)	71 (13.8)	71.1 (14.4)
Sex, male	58 (51.8%)	39 (52%)	30.5 (31.8%)	660 (60%)	110 (54.5%)
Severity (NIHSS),	TNK 0.1: 8	14.4 (2.3)	TNK: 12 (9-	5.7 (5.3)	TNK: 17 (12-
mean (SD) or	(5-11)		18)		22)
median (IQR)	TNK 0.25:		ALT: 11 (8-		ALT: 17 (12-
	10 (6-15)		16)		22)
	TNK 0.4: 9-				
	5-17)				
	ALT 13 (5-				
	17)				
Permitted time window	$\leq 3h$	$\leq 6h$	$\leq$ 4.5h	$\leq$ 4.5h	$\leq$ 4.5h
Onset to treatment,		176 (48)	188 (44.5)	TNK: 118	TNK: 125
mins, median		TNK 0.1	TNK: 180	(79-180)	(102-156)
(IQR) or mean		$3.1 \pm 0.9$	(156-215)	ALT: 111	ALT: 134
(SD)		TNK 0.25	ALT: 200	(80-174)*	(104-176)
		3.0+0.7	(160-220)		
		ALT 2.7+0.8			
Atrial fibrillation		28 (37.3%)	34 (35.4%)	119 (10.8%)	
Hypertension	89 (79.5)	47 (62.7%)	48 (50%)	482 (43.8%)	
Dyslipidemia	56 (50%)	37 (49.3%)	11 (11.5%)	126 (11.5%)	
Diabetes	21 (18.8%)	15 (20%)	14 (14.6%)	144 (13.1%)	
Current smoker	16 (14.2%)	15 (20%)	23 (24%)	346 (31.5%)	
Large vessel		77%	47%		100%
occlusion					

**Table 3:** Baseline characteristics of patients enrolled in the intravenous alteplase vs. control trials (top panel) vs. patients included in the intravenous tenecteplase vs. alteplase trials (bottom panel). Patients enrolled in the tenecteplase vs. alteplase trials had significantly less severe strokes (baseline NIHSS 6 vs. 12 on average), significantly more stroke mimics (15%), underrepresentation of females (40% in the tNK trials overall vs. 45% in the alteplase trials) and

Version 2.0

45

lower incidence of atrial fibrillation (14% in the tenecteplase trials vs. 24% in the alteplase trials), thus suggesting that tenecteplase vs. alteplase trial level meta-analysis does not represent well patients with acute stroke treated with intravenous alteplase.

Webtable 1: Baseline characteristics of IST-3 and 8 previous trials, overall and separately according to time to treatment

		≤3 hours		>	3, ≤4.5 hour	S		>4.5 hours			Total	
Baseline variable	8 previous trials	IST-3	p value	8 previous trials	IST-3	p value	8 previous trials	IST-3	p value	8 previous trials	IST-3	p value
Number randomised	929	620		1620	1148		1128	1266		3721	3035	
Treatment delay (hours)	2.2 (0.6)	2.4 (0.4)	< 0.0001	3.9 (0.4)	3.8 (0.4)	<0.0001	5.2 (0.6)	5.4 (0.5)	<0.0001	3.9 (1.2)	4.2 (1.2)	< 0.0001
Age (years)	67 (11)	83 (8)	<0.0001	65 (12)	79 (11)	<0.0001	66 (12)	73 (13)	<0.0001	66 (12)	77 (12)	< 0.0001
≤80	869 (94%)	114 (18%)	<0.0001	1589 (98%)	474 (41%)	<0.0001	1106 (98%)	830 (66%)	<0.0001	3606 (97%)	1418 (47%)	< 0.0001
>80	60 (6%)	506 (82%)		31 (2%)	674 (59%)		21 (2%)	436 (34%)		112 (3%)	1617 (53%)	
Stroke severity (NIHSS)	14 (7)	14 (7)	0.789	11 (6)	13 (7)	<0.0001	11 (6)	11 (7)	0.216	12 (6)	12 (7)	0.216
0-4	50 (5%)	54 (9%)	0.097	129 (8%)	139 (12%)	<0.0001	82 (7%)	207 (16%)	<0.0001	266 (7%)	400 (13%)	< 0.0001
5-10	284 (31%)	187 (30%)		687 (42%)	370 (32%)		483 (43%)	507 (40%)		1469 (39%)	1064 (35%)	
11-15	211 (23%)	124 (20%)		394 (24%)	237 (21%)		281 (25%)	240 (19%)		887 (24%)	601 (20%)	
16-21	219 (24%)	156 (25%)		300 (19%)	244 (21%)		190 (17%)	217 (17%)		715 (19%)	618 (20%)	
≥22	135 (15%)	99 (16%)		72 (4%)	158 (14%)		52 (5%)	95 (8%)		270 (7%)	352 (12%)	
Female	373 (40%)	368 (59%)	< 0.0001	637 (39%)	609 (53%)	<0.0001	462 (41%)	592 (47%)	0.004	1487 (40%)	1570 (52%)	< 0.0001
History of hypertension	559 (60%)	430 (69%)	0.0002	912 (56%)	723 (63%)	0.0003	622 (55%)	800 (63%)	<0.0001	2114 (57%)	1954 (64%)	< 0.0001
History of stroke	123 (13%)	142 (23%)	< 0.0001	222 (14%)	291 (25%)	<0.0001	195 (17%)	266 (21%)	0.024	544 (15%)	699 (23%)	< 0.0001
History of diabetes mellitus	186 (20%)	49 (8%)	< 0.0001	275 (17%)	133 (12%)	<0.0001	217 (19%)	206 (16%)	0.061	690 (19%)	388 (13%)	< 0.0001
History of atrial fibrillation	189 (20%)	237 (38%)	<0.0001	279 (17%)	360 (31%)	<0.0001	224 (20%)	316 (25%)	0.003	700 (19%)	914 (30%)	< 0.0001
Aspirin use	262 (28%)	320 (52%)	<0.0001	411 (25%)	460 (40%)	<0.0001	276 (24%)	526 (42%)	<0.0001	955 (26%)	1306 (43%)	< 0.0001
Weight (kg)	77.6 (16.5)	68.2 (13.5)	<0.0001	77.2 (15.1)	71.0 (14.5)	< 0.0001	75.9 (16.5)	74.8 (15.3)	0.080	76.9 (15.9)	72.0 (14.9)	< 0.0001
Systolic blood pressure (mmHg)	154 (22)	157 (24)	0.022	152 (20)	155 (24)	0.001	153 (21)	155 (24)	0.046	153 (21)	155 (24)	< 0.0001
Diastolic blood pressure (mmHg)	85 (14)	81 (15)	<0.0001	84 (13)	82 (14)	0.0001	84 (13)	83 (15)	0.039	84 (13)	82 (15)	< 0.0001

Categorical data presented as n (%), continuous data presented as mean (SD). The p-values can be used to identify the statistically, but not necessarily clinically, significant differences between patients in IST-3 and patients in the 8 earlier trials.

Baseline characteristics	Haley et al. [8]	Parsons et al. [9]	Huang et al. [12]	Logallo et al. [13]	Combined		p value
					Tenecteplase	Alteplase	
Age, mean (SD)	69.9 (15.7)	69 (8.9)	71 (12.5)	71 (13.8)	70.5 (14.2)	71.1 (13)	0.423
Male, n (%)	46 (56.7)	25 (50)	61 (63.5)	660 (60)	393 (58.5)	399 (60.8)	0.433
Hypertension, n (%)	64 (79)	31 (62)	48 (50)	482 (43)	324 (48.2)	301 (45.8)	0.409
Diabetes, n (%)	15 (18.5)	7 (14)	14 (14.5)	146 (13.2)	91 (13.5)	91 (13.8)	0.874
Hyperlipidemia, n (%)	30 (37)	24 (48)	11 (11.4)	126 (11.4)	103 (15.3)	98 (14.9)	0.878
Active smoker, $n$ (%)	14 (17.2)	6 (12)	23 (23.9)	346 (31.4)	194 (28.9)	195 (29.7)	0.763
Atrial fibrillation, n (%)	201000	19 (38)	34 (35.4)	119 (10.8)	82 (12.5)	90 (14.4)	0.368
Previous stroke/TIA, n (%)	19 (23.4)	-	23 (23.9)	239 (21.7)	146 (21.7)	135 (20.5)	0.638
Premorbid mRS $\geq$ 3, n (%)	-	0	0	62 (5.6)	27 (4.1)	35 (5.6)	0.243
Baseline NIHSS, mean (SD)	10.7 (8.5)	14.3 (2.3)	12.5 (5.9)	5.7 (5.3)	6.82 (6.2)	6.85 (5.9)	0.928
Onset to treatment time, mean (SD)		171 (45.9)	193 (45)	124 (72.4)	132.5 (74.2)	129 (70.3)	0.388
Stroke mimics, n (%)	2 (2.4)	0	7 (7.2)	190 (17.2)	99 (14.7)	93 (14.1)	0.815

\*Analysis of variance tests (ANOVA) were used to compare means for continuous variables and Chi square tests or fisher's exact test were used to compare proportions for categorical variables

SD standard deviation, TIA transient ischemic attack, mRS modified Rankin Scale, NIHSS National Institute of Health Stroke Scale

#### Figure 1: Exemplar labelling of intravenous tenecteplase and intravenous alteplase

p value\*

# INVESTIGATIONAL DRUG/DROGUE DE RECHERCHE

#### TENECTEPLASE (TNK) 50mg Vial \*\* DOSE 0.25mg/kg body weight\*\*

Sponsor: University of Calgary, [name] AcT Trial Protocol V1.5

CAUTION:To be used by qualified investigators only/ Reservee uniquement a l'usage de chercheurs competent

## INVESTIGATIONAL DRUG/DROGUE DE RECHERCHE

#### ALTEPLASE (TPA) 100mg Vial \*\* DOSE 0.9 mg/kg body weight\*\*

Sponsor: University of Calgary, [name] AcT Trial Protocol V1.5

CAUTION:To be used by qualified investigators only/ Reservee uniquement a l'usage de chercheurs competent

# Linkage rates for the QuICR Registry to Administrative Datasets

# Based on November 2018 QuICR Extract

	2015/16	2016/17	2017/18	2018/19 Q1
QuICR - DAD	97.7%	97.8%	96.7%	96.7%
QuICR – NACRS Community stroke presentations only	94.3%	97.3%	96.0%	94.7%

Linkage rates depend on the quality of QuICR and administrative data. If linkage rates do not meet acceptable standards, Analytics can supply project sponsors with an account of lost records for chart review. Some examples of relevant QuICR data quality issues are provided in the following table:

	2015/16	2016/17	2017/18	2018/19 Q1
Null PHN	0.96%	0.0%	1.26%	0.55%
Invalid DOB	0.19%	0.0%	1.95%	0.0%

*Source: QuICR Extract as of November 2018 (VW\_QUICR\_EXTRACT)* 

#### 1. Introduction

This Statistical Analysis Plan (SAP) is for the Alteplase Compared to Tenecteplase in patients with Acute Ischemic Stroke (AcT) Trial. Intravenous thrombolysis with alteplase is widely used in patients with acute ischemic stroke presenting early after symptom onset. Recent phase II trials have suggested that intravenous tenecteplase may be safer and potentially achieves higher early reperfusion rates than alteplase. This study investigates whether intravenous tenecteplase is non-inferior to intravenous alteplase with respect to clinical outcomes.

## 2. Trial Objectives

The Alteplase compared to Tenecteplase (AcT) trial will therefore seek to demonstrate the noninferiority of intravenous tenecteplase compared to intravenous alteplase in terms of 90-day functional outcome assessed using the modified Rankin Score. The secondary objectives of this study are to compare intravenous tenecteplase to alteplase in terms of safety and relevant secondary outcomes.

#### 3. Study Design

The AcT trial is a pragmatic, registry linked, prospective, randomized (1:1) controlled, openlabel parallel group clinical trial with blinded endpoint assessment of 1600 patients to test if intravenous tenecteplase (0.25 mg/kg body weight, max dose 25 mg) is non-inferior to intravenous alteplase (0.9 mg/kg body weight, max dose 90 mg) in patients with acute ischemic stroke otherwise eligible for intravenous thrombolysis as per standard care. The trial will recruit patients from the emergency departments of participating primary or comprehensive stroke centers across Canada. Study outcomes will be collected through the trial and/or through linkage to ongoing registries and national administrative databases.

#### 4. Randomization

Randomization will be centralized, secure and concealed using a real-time web-based server, to prevent confounding due to allocation bias. Investigators can access the randomizer either through the internet, secure text or through a local telephone. The trial will have allocation concealment and blinded endpoint assessment. Given the pragmatic design of the trial and the time sensitive nature of acute stroke, blinding the enrolling health personnel to treatment allocation is not practical. A 1:1 randomization will be used to allocate patients to intravenous tenecteplase (0.25 mg/kg body weight, max dose 25 mg) or intravenous alteplase (0.9 mg/kg body weight, max dose 90 mg). Randomization will use a validated minimal sufficient balance (MSB) algorithm to assure balance by site.

#### 5. Sample size

The primary outcome will be 90-day mRS score which will be determined by the Rankin Focused Assessment (RFA-A) method using centralized telephone interview by trained study personnel blinded to treatment allocation.

A total of 1600 subjects will be randomly assigned to receive either intravenous tenecteplase or

Page 3 of 9

alteplase in a 1:1 ratio, assuming a missingness of primary outcome data/loss to follow-up rate <5%. Based on prior literature, the incidence of primary outcome (mRS 0-1) 90 days after randomization is assumed to be 38% and 35% respectively for tenecteplase vs. alteplase. Assuming a one-sided non-inferiority margin of 5%, a one-sided significance Type I error of 2.5% and 90% power to show that tenecteplase is non-inferior to alteplase, 759 subjects are needed in each arm of the trial. The choice of 5% as a non-inferiority margin represents 50% of the estimate of effect size (10%) for intravenous alteplase administered within 3 hours of stroke symptom onset vs. control for the outcome mRS 0-1 measured at 90 days obtained from the largest patient level pooled meta-analysis of such data. The choice of 5% as the non-inferiority margin in this trial means that at least half of the point estimate of effect for intravenous alteplase vs. control will be preserved. Hence the non-inferiority margin is guaranteed to be less than the lowest reasonable estimate of alteplase vs. control (placebo) effect size.

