#### 4.3.1 The evidence for intravenous alteplase in patients with acute ischemic stroke

Intravenous (IV) thrombolysis with alteplase (single chain human recombinant tissue plasminogen activator) is the most widely used therapy in acute ischemic stroke patients presenting within the first 4.5 hours from symptom onset. The NINDS trial was the first RCT to show superiority of IV alteplase over placebo in improving clinical outcome when given within the first three hours of symptom onset. The ECASS III study further extended the treatment window up to 4.5 hours from symptom onset. The effect size was lower in patients treated beyond 3 hours with a Number Needed to Treat (NNT) increase by 1 for every 20 minutes delay in initiating alteplase. The value of faster thrombolysis was further emphasized in a patient level meta-analysis of all intravenous alteplase trials. This study demonstrated the time-dependent effectiveness of alteplase administration up to 4.5 hours from symptom onset. There was evidence of benefit in patients aged over 80, those with minor stroke deficits, and those with or without imaging documented intracranial occlusion. The rate of intracranial hemorrhage varied from 2.7-15.7% across the alteplase trials, depending on the definitions used for symptomatic hemorrhages in these different studies. The risk of alteplase related hemorrhage was higher among patients who had more severe strokes. The magnitude of benefit was dependent on the site of arterial occlusion with better recanalization seen in patients with distal occlusions.

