# 6. Statistics

#### 6.1 The proposed sample size and justification

The primary endpoint is the proportion of subjects that achieve a 90-day score of 0 or 1 on the mRS scale in both arms. The choice of this dichotomous outcome is based on clinical acceptance, an assessment of the distribution of mRS in the individual patient level meta-analysis and the choice of similar outcome in most ongoing trials.

A total of 1600 subjects will be randomly assigned to receive either intravenous tenecteplase or alteplase in a 1:1 ratio. Based on prior literature, we assume that the incidence of primary outcome (mRS 0-1) 90 days after randomization will be 38% and 35% respectively. Assuming a one-side non-inferiority margin of 5%, a one-sided significance Type I error of 2.5% and 90% power to show that tenecteplase is non-inferior to alteplase, we will need 759 subjects in each arm of the trial. The choice of 5% as a non-inferiority margin represents 50% of the estimate of effect size (10%) for intravenous alteplase administered within 3 hours of stroke symptom onset vs. control for the outcome mRS 0-1 measured at 90 days. This data from Emberson et al is the largest patient level

Version 2.0

26

pooling of data from all intravenous alteplase vs. control trials to date. The choice of 5% as the noninferiority margin in this trial means that at least half of the point estimate of effect for intravenous alteplase vs. control will be preserved. Additionally, the choice of 5% is strictly less than the lower CI bound of ~6% on the same point estimate in data from Emberson et al. Hence the non-inferiority margin is guaranteed to be less than the lowest reasonable estimate of alteplase vs. control (placebo) effect size.

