7.2. Per-protocol population

All patients enrolled in the trial who received any dose of study drug and met all the inclusion and exclusion criteria per current Canadian Stroke Best Practices Recommendations. Since the trial has pragmatic eligibility criteria, patients who may have been inadvertently enrolled and received thrombolysis beyond 4.5 hours from stroke onset and any treatment crossovers are defined as protocol deviations for analysis.

Page 4 of 9

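### The 5-point margin is derived from alteplase's effect within 3 hours, so the claim that at least half of that effect is kept does not carry over to a trial enrolling to about 4.5 hours

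*Combined protocol and SAP*

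**What the plan says.** Protocol 6.1 and SAP 5 justify the 5-point margin in the same way. It is half of a 10-point effect, and protocol 6.1 states that this effect is "for intravenous alteplase administered within 3 hours of stroke symptom onset vs. control for the outcome mRS 0-1 measured at 90 days". Both sections then say that at least half of the alteplase point estimate is kept; that sentence carries no time limit. Protocol 6.1 adds that 5 points lies below the lower confidence bound of about 6% on the same within-3-hour estimate. SAP 5 omits this step but keeps the conclusion: "Hence the non-inferiority margin is guaranteed to be less than the lowest reasonable estimate of alteplase vs. control (placebo) effect size".

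The enrolled population is wider than the one behind the margin:

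- Protocol 5.6 admits all patients eligible for alteplase under standard care and writes no hour limit.
- Protocol 4.1 describes alteplase as given to patients presenting up to 4.5 hours from onset.
- SAP 7.2 counts as deviations patients who "received thrombolysis beyond 4.5 hours from stroke onset", along with treatment crossovers.
- SAP 10 plans a subgroup split at 180 minutes from onset to needle.

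On how the effect changes with time, protocol 4.3.1 says: "The effect size was lower in patients treated beyond 3 hours".

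**The concern.** A preserved-effect argument is only as good as the match between the historical effect and the population in which the new drug is tested. Here the historical effect comes from the earliest-treated, most responsive patients, while the trial also enrols patients treated later. If alteplase's average benefit in the enrolled mix is below 10 points, 5 points is more than half of it.

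Non-inferiority is the main confirmatory claim, and protocol 4.6 expects it to change practice. Readers will take from the sample-size section that a positive result secures at least half of alteplase's benefit. The plan does not establish that for the patients it enrols.

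**Working it through.** **1. The plan's own sample size.** Inputs (SAP 5): "a one-sided significance Type I error of 2.5% and 90% power"; the outcome rate "is assumed to be 38% and 35% respectively for tenecteplase vs. alteplase"; margin 5 points.

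n per arm = (0.35×0.65 + 0.38×0.62) × (1.960 + 1.282)² / (0.03 + 0.05)² = 760.3, so 761 against the stated 759. Allowing 5% loss, 759/0.95 = 799 per arm, or about 1600 in total. The sample size reproduces and is not in question.

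**2. Slack in the margin.** 5/10 = 50% exactly. Let w be the share treated after 3 hours and e the alteplase effect (in points) in those patients.

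- Mixed effect: E = 10(1 − w) + e·w
- Smallest share preserved when the margin is met: 1 − 5/E

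For any w above 0 and any e below 10, E is below 10 and the share is below 50%. This needs only the protocol's statement that the late effect is lower, taking 10% as exact.

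**3. Size, as illustration.** The documents give neither e nor w for this trial, so both are assumptions.

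- *Late effect.* Protocol 4.3.1 says the NNT rises by 1 per 20 minutes of delay. In appendix Table 3, mean delay is 2.2-2.4 h in the early group and 3.8-3.9 h in the 3-4.5 h group, a gap of 84-102 minutes. Starting from NNT 10, the late NNT is 10 + 84/20 = 14.2 to 10 + 102/20 = 15.1, so e is about 7.0 to 6.6 points. The outcome and baseline behind the NNT rule are not stated.
- *Late share.* Taken as 25-60%. In appendix Table 2, the NOR-TEST upper quartiles of 180 and 174 minutes suggest about 25%, and the ATTEST medians of 180 and 200 minutes suggest half or more. The EXTEND-IA TNK upper quartiles (156 and 176 minutes) would suggest less than 25%.

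Results:

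- w = 25%, e = 7.04: E = 9.26; share = 1 − 5/9.26 = 46%
- w = 60%, e = 6.62: E = 7.97; share = 1 − 5/7.97 = 37%

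Other inputs:

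| w | e (points) | E | share preserved |
|---|---|---|---|
| 10% | 7 | 9.70 | 48.5% |
| 25% | 9 | 9.75 | 48.7% |
| 50% | 7 | 8.50 | 41.2% |
| 60% | 5 | 7.00 | 28.6% |
| 60% | 3 | 5.80 | 13.8% |

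**4. The SAP's inference.** The lower bound of a 10-point estimate is 10 − 1.96·SE. It exceeds 5 only if SE is below 5/1.96 = 2.55 points. Being half of the point estimate says nothing about SE. The 6% bound implies SE = (10 − 6)/1.96 = 2.04, so the step holds within 3 hours, but only with the figure that SAP 5 leaves out.

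**5. The lower bound for the mix.** Assume independent strata, SE 2.04 within 3 hours, and SE about 1.73 at 3-4.5 hours. The latter is √[(0.25×0.75 + 0.35×0.65)/1384], with 2768 patients from appendix Table 3 split evenly and rates of 25% and 35% assumed.

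Mixed bound = E − 1.96·√[((1 − w)·2.04)² + (w·1.73)²]:

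- w = 25%, e = 7: 6.1
- w = 50%, e = 7: 5.9
- w = 50%, e = 5: 4.9
- w = 60%, e = 5: 4.4

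The bound can fall on either side of 5.

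**The case against.** The plan states the within-3-hour basis openly, in the sentence just before the preservation claim. Read as a remark about that estimate alone, the claim is arithmetically true. The lower-bound premise is in the protocol, so its absence from the SAP is a drafting gap. The 4.5-hour limit is inferred from the description of standard care and the per-protocol definition, not written as a criterion. The decision rule concerns the confidence bound: by the protocol's own example, with alteplase at 35% a passing trial needs tenecteplase at 34.7% or better, so a pass means an observed difference near zero. Neither analysis section plans to report a preserved fraction. SAP 10 already looks at the primary outcome by onset-to-needle time.

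Most of this stands and limits the point to wording and supportive analysis. It does not rescue the unqualified claim. Read narrowly, the claim describes a different population from the one enrolled; read as written, it does not hold. A looser enrolment limit than 4.5 hours would not help.

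Stronger readings are tempting but unsupported:

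- *The guarantee is false.* The documents give no 0-4.5 hour bound, and on step 5's assumptions it lies above or below 5.
- *Only 17% is preserved* (1 − 5/6, against the 6% bound). The plan claims half of the point estimate, not of the bound.
- *Late-treated patients might keep none of the benefit.* This needs a late effect of 5 points or less, for which the documents give no figure, and it applies an overall margin to a stratum in which no non-inferiority claim is made.

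**Conclusion.** The point holds in two parts. First, the statement that at least half of alteplase's effect is kept fails for the enrolled mix. That rests only on 10% being exact, some patients being treated after 3 hours, and the protocol's statement that the effect is then lower. Second, the guarantee is not shown for that population, and in the SAP it also lacks its premise.

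The size is uncertain. A preserved share of about 37-46% depends on an assumed late share of 25-60% and an NNT rule used outside any stated context. A small late share brings it close to 50%, and the low values in the table need late effects that the documents do not support. Nothing here shows that 5 points is an indefensible margin, or that the sample size or primary test is wrong.

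**What to change.** Keep the margin, sample size and primary test. In protocol 6.1 and SAP 5:

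1. Limit the preservation statement and the 6% lower-bound argument to treatment within 3 hours.
2. Restore the 6% premise in SAP 5.
3. Replace the guarantee with a statement that this is not shown for the full enrolled population (about 0-4.5 hours). Alternatively, restate the margin against a 0-4.5 hour effect with its confidence bound.

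As a supportive analysis, report the risk difference with its 95% CI against −5 points in the planned subgroup with onset-to-needle time of 180 minutes or less. That clock, not time of randomisation, matches how the historical effect was defined. Optionally, report the preserved fraction using time-specific effects from the same pooled meta-analysis, weighted by the observed time mix. Label it supportive, since those effects are not in the documents and the mix is known only after enrolment.

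The cost is text edits, analyses of data already being collected, and a less favourable account of what the margin preserves. The subgroup analysis will be less precise. With 25-60% treated late, 600 to 320 per arm remain of 800. At the planning rates, the CI half-width is 1.96·√(0.4631/n) = 5.4 to 7.5 points, against 4.7 for the whole trial. It should therefore be presented as an estimate, not as a second test.
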